6. SAFETY

Safety will be assessed by summarizing the incidence and type of AEs and examining changes in laboratory parameters (hematology and chemistry), vital signs, and suicidal ideation and behavior as measured by the C-SSRS (Columbia-Suicide Severity Rating Scale).

In all the safety analysis, randomized participants who received at least 1 (partial or complete) dose of study agent administration will be included and analyzed according to the treatment they actually received, regardless of the treatments they are randomized to. No formal statistical comparison is planned.

Depending on the safety data categories, the cumulative safety data will be analyzed through different study periods through Week 16 and Week 48. Unless otherwise specified, tabular summaries of safety events for key study periods are in general presented as following:

Summaries through Week 16 (placebo controlled):

Safety data through Week 16 will be summarized by treatment groups

1. Placebo
2. Guselkumab 200 mg SC
3. Guselkumab 1200 mg IV
4. Combined Guselkumab

This allows between-group comparisons of safety between the guselkumab regimens and the placebo group based on similar follow-up period in each group.

Summaries through Week 48

Safety data through Week 48 will be summarized by treatment groups including

1. Placebo → guselkumab 100 mg SC
2. Placebo → guselkumab 200 mg SC
3. Guselkumab 200 mg SC
4. Guselkumab 1200 mg IV
5. Combined Guselkumab

This allows safety comparisons between each guselkumab regimen through Week 48 based on the similar follow-up time in each group.

The list of actual treatment groups for safety analyses and inclusions of participants and safety events/measurements in each group are defined as follows:

1. **Placebo:** all participants who were randomized to placebo at Week 0 and received treatment with placebo only or received treatment with placebo prior to receiving treatment with guselkumab. For participants who started treatment with placebo but later received

guselkumab, the safety events/measurements on and after the first dose of guselkumab will be excluded from this group. Only the safety events/measurements that occurred while the participants had been receiving placebo only will be included in this group.

2. **Placebo → guselkumab 100 mg SC:** all participants who were randomized to placebo at Week 0 started treatment with placebo only and later randomized to treatment with guselkumab 100 mg SC q8w. Only the safety events/measurements from these participants that occurred on and after their first administration of guselkumab will be included in this group.
3. **Placebo → guselkumab 200 mg SC:** all participants who were randomized to placebo at Week 0 started treatment with placebo only and later randomized to treatment with guselkumab 200 mg SC q4w. Only the safety events/measurements from these participants that occurred on and after their first administration of guselkumab will be included in this group.
4. **Guselkumab 200 mg SC:** all participants who were randomized to guselkumab 200 mg SC q4w at Week 0 and received guselkumab. All the safety events/measurements from these participants that occurred from Week 0 will be included in this group.
5. **Guselkumab 1200 mg IV:** all participants who were randomized to guselkumab 1200 mg IV q4w at Week 0 and received guselkumab. All the safety events/measurements from these participants that occurred from Week 0 will be included in this group.

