1.2. Trial Design

This is a Phase 2, multicenter, randomized, placebo-controlled, double-blind, proof-of-concept (POC) study evaluating the efficacy, safety, PK, and immunogenicity of SC and IV administered guselkumab for the treatment of moderate to severe HS in adult participants. The participant population will comprise men and women who have had moderate to severe HS for at least 1 year.

A diagram of the study design ([Figure 1](#)) is provided below and as depicted in [Figure 1](#), approximately 180 participants who satisfy all inclusion and exclusion criteria will be randomized in a 1:1:1 ratio to 1 of 3 groups:

Group 1: Guselkumab Regimen 1 (1200 mg IV q4w x 3 → 200 mg SC q4w)

Participants will receive guselkumab 1200 mg IV at Week 0, Week 4, and Week 8 (ie, a total of 3 IV guselkumab doses and 3 SC placebo doses). At Week 12, participants will continue treatment with guselkumab 200 mg SC q4w through Week 36.

Group 2: Guselkumab Regimen 2 (200 mg SC q4w x 3 → 200 mg SC q4w)

Participants will receive guselkumab 200 mg SC at Week 0, Week 4, and Week 8 (ie, a total of 3 SC guselkumab doses and 3 IV placebo doses). At Week 12, participants will switch treatment to guselkumab 200 mg SC q4w through Week 36.

Group 3: Placebo

[figure not shown]
Participants will receive placebo IV and SC at Week 0, Week 4, and Week 8 (ie, a total of 3 IV and 3 SC placebo doses) and an additional SC placebo dose at Week 12. At Week 16, participants will be rerandomized in a 1:1 ratio to either guselkumab 200 mg SC q4w through Week 36 or guselkumab 100 mg SC at Weeks 16, 20, 28, and 36, and placebo at Weeks 24 and 32.

A screening period will take approximately 4 weeks. All participants will enter safety follow-up after Week 36 through Week 48. Two planned database locks (DBLs) will occur, at Week 16 and at Week 48.

Efficacy assessments (HS-IGA, lesion counts, Hurley staging, Hidradenitis Suppurativa Symptom Diary [HSSD], Dermatology Life Quality Index [DLQI], Hospital Anxiety and Depression Scale [HADS], and Patient's Global Impression of Change [PGIC]) will be performed according to the Schedules of Activities. Serum samples for PK, immunogenicity, and biomarker analyses will be collected at the timepoints shown in the Schedules of Activities (Section 1.3 of the protocol).

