4.4. Extent of Exposure

The exposure data through Week 16 and through Week 36 will be summarized. The number and percentage of participants who receive study agent will be summarized by treatment group for the safety analysis set. Descriptive statistics will be presented for the following parameters:

- Number of administrations
- Cumulative total dose

Study agent lots received by treatment, including matching placebo for active treatment will be summarized.

In addition, the average exposure (number of administrations) and average duration of follow-up (weeks) will also be summarized by treatment group in the safety tables through different study time periods.

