- The incidence and type of infections.
- The incidence and type of reasonably related AEs.
- The incidence and type of AEs temporally associated with infusion (defined as an AE that occurred on the same day of infusion, with a start time during infusion or ≤ 60 minutes after the end of infusion).
- The incidence and type of injection-site reactions.

These summary tables will provide the count and percentage of participants with 1 or more of the specified AEs by treatment group. In addition to the summary tables, listings will be provided for participants who:

- Had SAEs.
- Had AEs leading to discontinuation of study agent administration.
- Had AEs of severe intensity.
- Had treatment-emergent adverse events temporally associated with infusion.
- Had anaphylactic or serum sickness-like reactions.

Since safety should be assessed relative to exposure and follow-up, most AE summary tables will include average weeks of follow-up and average number of study agent administrations, infusions and injections for each treatment group. A listing of participants who died will be provided.

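### SAP Section 6 says the through-Week-48 safety groups have similar follow-up, but its own definitions give at most about 32 weeks in the crossover groups and about 48 in the Week 0 groups

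*SAP*

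**What the plan says.** SAP Section 6 lists five columns for the through-Week-48 safety tables: placebo to 100 mg SC, placebo to 200 mg SC, 200 mg SC, 1200 mg IV, and Combined Guselkumab. It then states: "This allows safety comparisons between each guselkumab regimen through Week 48 based on the similar follow-up time in each group".

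The definitions later in the same section set when counting starts. For each crossover group: "Only the safety events/measurements from these participants that occurred on and after their first administration of guselkumab will be included in this group". For each group on guselkumab from the start: "All the safety events/measurements from these participants that occurred from Week 0 will be included in this group". Combined Guselkumab does not appear among these definitions.

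SAP Section 1.2 fixes the calendar. Placebo participants cross over at Week 16 ("At Week 16, participants will be rerandomized in a 1:1 ratio to either guselkumab 200 mg SC q4w through Week 36", or to the 100 mg regimen), and follow-up has one end for everyone: "All participants will enter safety follow-up after Week 36 through Week 48".

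For adverse events, SAP Section 6.1 plans crude proportions: "These summary tables will provide the count and percentage of participants with 1 or more of the specified AEs by treatment group". The same section accepts that length of observation matters: "Since safety should be assessed relative to exposure and follow-up, most AE summary tables will include average weeks of follow-up". SAP Section 4.4 likewise says that "average duration of follow-up (weeks) will also be summarized by treatment group in the safety tables through different study time periods". Section 6 plans no formal safety comparison.

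**The concern.** A percentage with at least one event can be compared between groups only if the groups are observed for similar lengths of time. Section 6 says that they are, for every regimen. Its definitions say otherwise whenever a crossover group is set against a Week 0 group.

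The contrasts affected are ones that readers will want to make. The 100 mg regimen exists only as a crossover group, so comparing its safety with 1200 mg IV always sets the shorter window against the longer one. The same holds for 200 mg after placebo against 200 mg from Week 0. In each case the crossover group could show a lower percentage because of its shorter window alone. Safety and tolerability are part of the primary objective, so these tables will be read closely even though nothing in them is tested.

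**Working it through.** **Planned counted follow-up** (SAP Sections 1.2 and 6)

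- Crossover groups: Week 48 − Week 16 = 32 weeks.
- Week 0 groups: Week 48 − Week 0 = 48 weeks.
- Difference 16 weeks; ratio 48/32 = 1.5.

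The SAP gives no number for follow-up, only the word similar, and 32 against 48 does not fit it. The word does fit the through-Week-16 tables (16 weeks planned in all groups) and comparisons within each pair. Both figures are planned maxima, because Protocol Section 7.1 follows participants who stop study intervention for about 12 weeks after their last dose.

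**Effect on a crude percentage.** The documents give no adverse event incidence, hazard shape or dropout rate, so I assume 48-week percentages of 10, 30 and 60% and the same hazard in all groups. Let P48 be the 48-week percentage and H = −ln(1 − P48).

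- Constant hazard: P32 = 1 − exp(−H × 32/48).
- Half of H just after the first dose, the rest constant: P32 = 1 − exp(−H × (0.5 + 0.5 × 32/48)).
- Constant hazard, a share d of Week 0 participants followed only 12 weeks, crossover follow-up complete: Week 0 percentage = (1 − d) × P48 + d × (1 − exp(−H × 12/48)).

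| Scenario | P48 = 10% | P48 = 30% | P48 = 60% |
|---|---|---|---|
| Constant hazard: 32-week percentage | 6.8 | 21.2 | 45.7 |
| Gap, points | 3.2 | 8.8 | 14.3 |
| Half the hazard early: 32-week percentage | 8.4 | 25.7 | 53.4 |
| Gap, points | 1.6 | 4.3 | 6.6 |
| Constant hazard, d = 10%: gap, points | 2.5 | 6.7 | 10.3 |
| Constant hazard, d = 20%: gap, points | 1.7 | 4.5 | 6.4 |

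If all events fell just after the first dose, there would be no gap.

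**Could dropout equalize follow-up?** With complete crossover follow-up, mean follow-up is equal when d = (48 − 32)/(48 − f), where f is the follow-up in weeks of those who leave. For f = 0, 12 and 16 this gives d = 33%, 44% and 50%.

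**Combined column.** If it pools all four groups, with 120 Week 0 and 60 crossover participants, planned mean follow-up is (120 × 48 + 60 × 32)/180 = 42.7 weeks.

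**Precision of an exposure-adjusted rate.** About 30 participants per crossover group give at most 30 × 32 × 7/365.25 = 18.4 patient-years. Three participants with an event would give 3/18.4 = 16.3 per 100 patient-years, exact Poisson 95% CI 3.4 to 47.7.

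**Where the rate misleads.** With half of H just after the first dose and P48 = 30%, participants with a first event divided by time at risk is 53.1 per 100 patient-years over 32 weeks and 42.6 over 48 weeks, although the hazards are identical.

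**The case against.** The strongest reply is that the proven error is one explanatory sentence that drives no computation. The definitions beneath it are explicit, and correcting it changes no existing table. No formal comparison is planned, and the placebo-controlled contrast sits in the Week 16 tables, where follow-up is similar. Most adverse event tables will carry average weeks of follow-up and average numbers of administrations, so a reader would normally see roughly 32 against 48 weeks. The exposure-adjusted rate is imprecise in groups of about 30, can mislead if events come early, and does not remove the difference in time off dosing. The size of the gap rests on assumed inputs.

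Much of this stands. The imbalance is not hidden, no inference depends on it, and the only document-derived figure is 32 against 48 weeks. It does not rescue the sentence. Displaying mean follow-up discloses the imbalance but leaves the percentages unadjusted, and the displayed averages would contradict the text that invites the comparison. Section 6.1 already accepts the principle that safety be read against exposure.

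SAP Section 2.4 also plans selected safety analyses at the Week 16 lock, using whatever later data exist by then. Follow-up in those tables will be incomplete, so 32 and 48 weeks must be worded as maxima.

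**Conclusion.** The statement is wrong as written for any comparison between a crossover group and a Week 0 group: planned counted follow-up is at most about 32 against about 48 weeks. It is sound within each pair (100 mg against 200 mg crossover; 200 mg SC against 1200 mg IV).

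That conclusion needs only the SAP's own definitions and calendar. The effect on percentages is an illustration under equal hazards. In the scenarios shown it runs from no gap, if all events follow the first dose at once, to 14.3 points, with a constant hazard, no dropout and 60% at 48 weeks. The change should be made, but the weight is moderate because the tables are descriptive. The missing definition of Combined Guselkumab would by itself be only a matter of detail.

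**What to change.** 1. **SAP Section 6, the sentence.** Replace it with the planned counted follow-up per group (at most about 32 weeks in the crossover groups, about 48 in the Week 0 groups), and state that only comparisons within each pair rest on similar follow-up.
2. **SAP Section 6, Combined Guselkumab.** State which groups it pools. If all four, note that it mixes both windows.
3. **SAP Section 6.1.** For through-Week-48 adverse events, serious adverse events and infections, prespecify exposure-adjusted incidence beside the crude percentages: participants with a first event per 100 patient-years at risk, with 95% CI. State that intervals will be wide in the crossover groups and that the adjustment is exact only under a roughly constant hazard.
4. **Optional.** Add a supplementary table of the first 32 weeks from first guselkumab. It should note that the crossover window includes about 12 weeks after the last dose while the Week 0 groups are still being dosed, and that crossover participants are those who stayed through Week 16.

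The cost is one sentence, one definition and a few table columns from dates already collected. The drawback is a rate that is imprecise and can over-correct when events come early, which is why the crude percentages stay alongside it.

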9.3. Populations for Analyses

For the efficacy analyses in this study, the full analysis set (FAS) will be used according to the participants' assigned treatment to which they were randomized, regardless of the treatment they actually received. The FAS includes all randomized participants who receive at least one administration of study intervention. The FAS will be used for all primary and secondary efficacy analyses.

Safety analyses will include all participants who received at least 1 dose (complete or partial) of study intervention and participants will be analyzed based on the treatment they actually received, regardless of the treatment groups to which they were assigned.

Pharmacokinetics analyses for guselkumab will include participants who receive at least one complete dose of guselkumab and have at least one post-dose sample collection. Antibodies to guselkumab will be analyzed for participants who receive at least one dose of guselkumab and have at least one post-dose sample collection.

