9.4.3. Safety Analyses

Safety data, including but not limited to, AEs, SAEs, infections, serious infections, mortality, changes in laboratory assessments, and changes in vital signs will be summarized. Intervention-emergent AEs will be summarized by treatment group and Medical Dictionary for Regulatory

Activities (MedDRA) system organ class and preferred terms. Details will be specified in the SAP.

Safety Definition

Injection-Site Reactions

An injection-site reaction is any unfavorable or unintended sign that occurs at an injection-site and will be recorded as an AE. Detailed instructions for the evaluation of injection-site reactions are in the Trial Center File.

Adverse Events

The verbatim terms used in the eCRF by investigators to identify AEs will be coded using the MedDRA. Intervention-emergent AEs are AEs with onset during the intervention period or that are a consequence of a pre-existing condition that has worsened since baseline. All intervention-emergent AEs will be included in the analysis. For each AE, the percentage of participants who experience at least 1 occurrence of the given event will be summarized by intervention group. In addition, comparisons between intervention groups will be provided if appropriate.

Summaries, listings, datasets, or participant narratives may be provided, as appropriate, for those participants who die, who discontinue intervention due to an AE, or who experience a severe or a SAE.

The following analyses will also be used to assess the safety of participants in the study:

- The incidence and type of AEs.
- The incidence and type of SAEs.
- The incidence and type of infections.
- The incidence and type of reasonably related AEs.
- The incidence and type of injection-site reactions.
- The incidence and type of AEs temporally associated with infusion (defined as an AE that occurred on the same day of infusion, with a start time during infusion or ≤ 60 minutes after the end of infusion).
- The laboratory parameters and change from baseline in selected laboratory parameters (hematology and chemistry).
- The incidence of abnormal laboratory parameters (hematology and chemistry).

Listings of participants with SAEs and anaphylactic reaction/serum sickness reactions will also be provided. All safety analyses will be based on the population of participants who received at least 1 administration of study intervention; participants will be summarized by the intervention they received.

Clinical Laboratory Tests

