2.4.2. Safety Analysis Set

The safety analysis set includes all randomized participants who received at least 1 (partial or complete) dose of study agent, i.e., the treated population.

In the safety analyses, participants will be analyzed according to the treatment they actually received, regardless of the treatments they are randomized to.

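### SAP 6 promises safety analysis by treatment received, but its five defined columns all require the randomised arm, so mis-dosed participants are misplaced or unassigned in the summary tables

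*SAP*

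**What the plan says.** The as-treated principle is stated four times. SAP 2.4.2 takes every randomised participant with at least one full or partial dose and says "participants will be analyzed according to the treatment they actually received, regardless of the treatments they are randomized to". The opening of SAP 6 repeats it. Protocol 9.3 has "participants will be analyzed based on the treatment they actually received, regardless of the treatment groups to which they were assigned", and protocol 9.4.3 has "participants will be summarized by the intervention they received".

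SAP 6 then introduces its columns with the sentence "The list of actual treatment groups for safety analyses and inclusions of participants and safety events/measurements in each group are defined as follows". The five definitions are:

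- **Placebo:** "all participants who were randomized to placebo at Week 0 and received treatment with placebo only", or who had placebo before guselkumab. Events from the first guselkumab dose onward are excluded.
- **Placebo → 100 mg SC** and **Placebo → 200 mg SC:** randomised to placebo, started on placebo, later re-randomised to that dose. Events count from the first guselkumab dose. Receipt of the re-randomised dose is not required.
- **Guselkumab 200 mg SC:** "all participants who were randomized to guselkumab 200 mg SC q4w at Week 0 and received guselkumab". All events from Week 0 count.
- **Guselkumab 1200 mg IV:** the same form, with the other arm.

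Combined Guselkumab appears in the Week 16 and Week 48 layouts but has no definition.

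The SAP foresees dosing errors elsewhere. SAP 4.3 plans a table of randomised against actual treatment. SAP 4.5 lists wrong treatment or dose as a major deviation. SAP 2.4.1.2 removes placebo participants given guselkumab before Week 16 from the per-protocol set. SAP 7.1.1.1 excludes by-visit PK data after an incorrect agent.

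**The concern.** For a mis-dosed participant, a programmer cannot follow both the principle and the definitions. The two active columns ask only whether some guselkumab was received, so the regimen actually given cannot change the column. Nothing else in the SAP derives an actual-treatment group or says which text prevails.

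Attribution matters because the two regimens are far apart. Protocol Appendix 8 predicts a Cmax of 250 µg/mL after the third 1200 mg IV dose and 19.5 µg/mL at steady state on 200 mg SC (250/19.5 = 12.8-fold). Weekly AUC is 1070 against 92.8 µg·day/mL (1070/92.8 = 11.5-fold). Safety and tolerability are part of the primary objective. If some treated participants fit no column, the columns no longer add up to the safety analysis set. If the conflict is settled after unblinding, the choice is made with treatment and events in view.

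**Working it through.** No figure in the plan underlies this point, so there is none to reproduce. The check applies the five SAP 6 definitions literally to patterns of assignment and receipt.

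| Assigned | Received | Column under SAP 6 |
|---|---|---|
| Any | As assigned | Correct |
| 200 mg SC | 1200 mg IV × 3, then 200 mg SC | 200 mg SC |
| 1200 mg IV | 200 mg SC throughout | 1200 mg IV |
| Placebo, re-randomised to 100 mg | Placebo, then 200 mg from Week 16 | Placebo → 100 mg from first guselkumab dose |
| Placebo | Guselkumab at Week 0 | None of the five |
| 200 mg SC or 1200 mg IV | Placebo only | None of the five |
| Placebo | Placebo at Week 0, guselkumab in error before Week 16, not re-randomised | Placebo up to that dose, then none |
| Placebo, later re-randomised to 100 mg | Placebo at Week 0, guselkumab in error before Week 16, then 100 mg | Placebo up to the error; no defined Week 16 column after it; Placebo → 100 mg in the Week 48 tables |
| 200 mg SC or 1200 mg IV | Placebo at Week 0, then as assigned | Assigned guselkumab column, all events from Week 0 |

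Reasons for the unassigned rows:

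- **Placebo participant given guselkumab at Week 0:** had neither placebo only nor placebo first, did not start on placebo as the crossover columns require, and was not randomised to guselkumab.
- **Guselkumab participant given only placebo:** fails the receipt condition of the active columns and the randomisation condition of the placebo columns.
- **Early guselkumab in a placebo participant:** the Placebo column stops at that dose, and the Week 16 layout has no crossover column.

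Whether Combined Guselkumab would catch the first and third cases cannot be decided, because it is undefined.

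Scale, with 60 per arm (SAP 1.4):

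- One participant in a main column: 1/60 = 1.7 percentage points.
- Crossover column, if all 60 placebo participants are re-randomised 1:1: 60/2 = 30, and 1/30 = 3.3 percentage points.

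These are shifts in an incidence, other things equal, when the misplaced participant has the event being tabulated.

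**The case against.** Several points on the other side stand.

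- **The definitions are hybrids.** A reader might infer that safety is simply analysed as randomised. The documents do not support that: each definition also carries a condition on treatment received or started, and the Placebo column's cut at the first guselkumab dose is a genuine as-treated rule.
- **Serious events do not vanish.** A reader might infer that events after a dosing error are lost from the report. SAP 6.1 says all reported treatment-emergent events enter the analysis. It also plans listings of serious events, severe events, events leading to discontinuation, infusion-associated events, anaphylactic or serum sickness-like reactions, and deaths. The deviation summaries show mis-dosed participants too. The gap is column placement in summary tables.
- **A full regimen swap is unlikely.** At Weeks 0, 4 and 8 every participant has both an infusion and injections. Receiving the other active regimen needs both to be wrong. A single wrong kit gives both actives or neither. Kits are assigned centrally and given on site.
- **No test is touched.** SAP 6 plans no formal safety comparison, so power and alpha are unaffected.

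These points limit the size. They do not remove the contradiction, because nothing ranks the general statement above the definitions. Single-kit errors also show that a rule for mixed exposure is needed.

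**Conclusion.** The point holds as a conflict between a stated principle and the definitions meant to carry it out. It is small. It touches only mis-dosed participants, whose number the documents do not give, and with none nothing changes. Each one is worth up to 1.7 points in a 60-participant column, or 3.3 points in a crossover column of about 30. The first figure assumes the planned arm size; the second also assumes that all placebo participants are re-randomised. What could go without a defined column and without one of the listings is mainly mild or moderate, non-serious events. The documents do not support a claim that safety results are materially biased or that serious events would be hidden.

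**What to change.** Change SAP 6 before unblinding:

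1. In the five definitions, replace the randomised-arm conditions with the study regimen actually received.
2. Add one prespecified rule for mixed exposure. It should cover a single erroneous administration, both actives or neither at a visit, and guselkumab given to a placebo participant before Week 16.
3. Define Combined Guselkumab as all participants from their first guselkumab administration.

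The aim is that every treated participant and every treatment-emergent event has a column in each table covering that exposure. The Week 48 layout has no placebo column, so the rule should say where a guselkumab-arm participant given only placebo appears there.

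Keying columns to the first administration alone would not be enough. A 1200 mg IV participant given 200 mg SC in error only at Week 0 would move wholly to the 200 mg column. A placebo participant given 1200 mg IV in error at Week 4 would still fit no regimen column after that dose.

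The cost is SAP wording and the matching programming specification. Design, sample size, testing and conduct do not change.
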